Part 2C: 2L+ participants with histological or cytological diagnosis of locally advanced or metastatic TNBC showing high B7-H4 expression (see [Section 8.6.2.1](#)) who have progressed after at least 1L of SOC chemotherapy and 1 line of SOC systemic therapy (eg, chemotherapy in combination with a checkpoint inhibitor if PD-L1 positive or chemotherapy alone if PD-L1 negative/low). De novo paired pre- and on-treatment biopsies are mandatory for approximately 5 participants.

4. Participants have at least 1 measurable lesion as defined by RECIST version 1.1 that has not been previously irradiated. For Part 1 dose escalation, participants with metastatic HR+ HER2- breast cancer with non-measurable but evaluable disease may be eligible after discussion with and approval from the sponsor.
5. Participants must be able to provide archival FFPE material containing tumor that is of diagnostic quality and representative of their diagnosed malignancy or consent to undergo a fresh biopsy during screening. 10 participants enrolling in Part 2B, and 5 participants enrolling in each of Parts 2A and 2C must agree to paired pre- and on-treatment biopsies. Ability of a participant to undergo biopsy safely should be determined during screening. Exceptions that biopsies cannot be obtained due to safety risk should be discussed and approved by the sponsor.
6. Participants with HR+ HER2- advanced or metastatic BrCa must have:
 - a. Documentation of ER or PR-positive tumor ($\geq 1\%$ positive stained cells) based on most recent tumor tissue utilizing an assay consistent with local standards and ASCO/CAP guidelines ([Allison et al, 2020](#))
 - b. Documentation that tumor is HER2-negative as determined by IHC score of 0/1+ or negative by *in situ* hybridization (FISH/CISH/SISH/DISH) defined as HER2/CEP17 ratio < 2 or for single probe assessment a HER2 copy number < 4 , consistent with ASCO/CAP guidelines ([Wolff et al, 2018](#)).
7. Participants with TNBC must have documentation that tumor tissue is negative ($< 1\%$ cells with nuclear positivity) for ER and PR as well as negative for HER2 as determined by IHC score of 0/1+ or negative by ISH (FISH/CISH/SISH/DISH) defined as a HER2/CEP17 ratio < 2 or for single probe assessment a HER2 copy number < 4 , consistent with ASCO/CAP guidelines ([Wolff et al, 2018; Allison et al, 2020](#)).

Informed Consent:

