9.2. Analysis Sets

For purposes of analysis, the following analysis sets are defined.

Participant Analysis Set	Description
Full Analysis Set (FAS)	All enrolled participants.
Safety Analysis Set (SAS)	All enrolled participants who receive at least 1 dose of study intervention. Unless otherwise specified the safety analysis set will be the default analysis set used for all analyses.
Per Protocol Analysis Set	All enrolled participants who do not have major protocol deviations during the course of the study
DLT Evaluatable Set	All enrolled participants who had at least 1 dose of study treatment and either experienced DLT or do not have major protocol deviations during the DLT observation period.
mITT Population	All enrolled participants who have received at least 1 dose of study medication; have a baseline assessment and at least 1 post baseline assessment;
PK Parameter Set	All enrolled participants treated who do not have protocol deviations influencing PK assessment and have sufficient information to estimate at least 1 of the PK parameters of interest.
PK Concentration Set	All enrolled participants who are treated and have at least 1 analyte concentration above the lower limit of quantitation.
Response Evaluatable Set	All enrolled participants who received at least 1 dose of study treatment and had adequate baseline disease assessment. Participants who discontinued early or died will be included.
Pharmacodynamic/ Biomarker Analysis Set(s)	The Pharmacodynamic/Biomarker analysis population is defined as all enrolled participants with at least 1 of the Pharmacodynamic/Biomarkers evaluated at pre and/or post dose.
Immunogenicity Analysis Set	The immunogenicity analysis set includes all enrolled participants who received at least 1 dose of study treatment and have at least 1 sample tested for ADA.

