### **3.3 Tertiary/Exploratory Endpoint(s)**

#### **Part 1**

#### **Efficacy Analysis**

Response Evaluable Set will be used for ORR and PFS (RECIST, irRECIST). Tumor response will be presented in the form of participant data listings that include, but are not limited to tumor type, tumor response at each visit, and best overall response.

Data will be summarized (also graphically where appropriate) and listed by dose level.

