**Table 1. Analysis Sets**

Participant Analysis Set	Description
Full Analysis Set (FAS)	All enrolled participants.

Participant Analysis Set	Description
Safety Analysis Set (SAS)	All enrolled participants who receive at least 1 dose of study intervention. Unless otherwise specified the safety analysis set will be the default analysis set used for all analyses.
Per Protocol Analysis Set	All enrolled participants who do not have major protocol deviations during the course of the study
DLT Evaluable Set	All enrolled participants who had at least 1 dose of study treatment and either experienced DLT or do not have major protocol deviations during the DLT observation period and received either 100% of dosing in cycle 1 (no priming regimen) or 100% of dosing in cycle 1 and cycle 2 (priming regimen)..
mITT Population	All enrolled participants who have received at least 1 dose of study medication; have a baseline assessment and at least 1 post baseline assessment;
Response Evaluable set	The response evaluable population will include all participants who received at least one dose of study treatment and had measurable disease at baseline and at least one post baseline disease assessment.
PK Parameter Set	All enrolled participants treated who do not have protocol deviations influencing PK assessment and have sufficient information to estimate at least 1 of the PK parameters of interest.
PK Concentration Set	All enrolled participants who are treated and have at least 1 analyte concentration above the lower limit of quantitation.

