### 6.2.4 Efficacy Analysis

Response Evaluable Set will be used for all response-related analyses including ORR, DoR, PFS, and TTP (RECIST, irRECIST). Tumor response will be presented in the form of participant data listings that include, but are not limited to tumor type, tumor response at each visit, and best overall response. Immune related response by irRECIST will be calculated and reported similarly to RECIST response. OS will be reported on the Full Analysis Set as well as on the mITT.

Data will be summarized (also graphically where appropriate) and listed by expansion cohort.

- **Overall Response Rate (ORR)**

- Overall response rate (ORR) is defined as the proportion of patients with a BOR of confirmed CR or confirmed PR by Investigator assessment in intracranial metastasis and extracranial lesions per mRECIST v1.1 (or RANO for glioblastomas) and RECIST v1.1, respectively.

- **Duration of Response (DOR)**

- Duration of response is defined as the time from start date (which is the date of first documentation of PR or CR) to date of first documentation of objective progression or death. Both confirmed DOR and unconfirmed DOR (uDOR) will be determined and reported separately for the subset of participants with a confirmed and unconfirmed objective response of CR or PR (defined below). DOR will be derived for Intracranial/RANO response rate, extracranial response rate and ORR.

- **Best Overall Response (BOR)**

- **Complete Response (CR):** Two objective statuses of CR a minimum of 4 weeks apart documented before PD.
- **Partial Response (PR):** Two objective statuses of PR or better (PR followed by PR or PR followed by CR) a minimum of 4 weeks apart documented before PD, but not qualifying as CR. Sequences of PR- Stable- PR are considered PRs as long as the two PR responses are observed at a minimum of 4 weeks apart.
- **Stable Disease (SD) (applicable only to patients with measurable disease at baseline):** At least one objective status of stable disease or better documented at least 6 weeks after start of treatment and before PD but not qualifying as CR or PR.
- **Non-CR/non-PD (applicable only to patients with non-measurable disease at baseline):** at least one non-CR/non-PD assessment (or better) documented at least 5 weeks after start of treatment and before first documentation of PD (and not qualifying for CR or PR).

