- **Progressive Disease (PD):** Progression documented within 12 weeks after 'start date' and not qualifying as CR, PR or SD.
- **Not Evaluable (NE):** All other cases. Note that reasons for NE should be summarized and the following reasons could be used:
  - No adequate baseline assessment
  - No evidence of disease at baseline
  - No post-baseline assessments due to early death, i.e., death prior to 6 weeks after 'start date'.
  - No post-baseline assessments due to other reasons
  - All post-baseline assessments have overall response NE
  - New anti-cancer therapy started before first post-baseline assessment
  - SD of insufficient duration (<5 weeks after 'start date' without further evaluable tumor assessments)
  - PD too late (>12 weeks after start of treatment)
  - Special and rare cases where BOR is NE due to both SD of insufficient duration ('too early') and late PD will be classified as 'SD of insufficient duration.'

- Unconfirmed CR (uCR) is defined as one objective status of CR documented before PD.
- Unconfirmed PR (uPR) is defined as one objective status of PR documented before PD but not qualifying as uCR.

Note: An objective status of PR, SD, or Non-CR/Non-PD cannot follow one of CR. SD can follow PR only in the rare case that tumor increases by less than 20% from the nadir, but enough that a previously documented 30% decrease from baseline no longer holds. If this occurs the sequence PR – SD – PR is considered a confirmed PR. A sequence of PR – SD – SD – PD would be a best response of SD if the window for SD definition has been met.

Patients with a BOR of “Not Evaluable” (NE) based on confirmed responses will be summarized by reason for having unknown status. The following reasons will be used:

- No adequate baseline assessment.
- No post-baseline assessments due to early death .
- No post-baseline assessments due to COVID-19 (ie, patients miss tumor assessment visits due to COVID-19 pandemic).
- No post-baseline assessments due to other reasons.
- All post-baseline assessments have overall response NE.
- New anticancer therapy started before first post-baseline assessment.
- SD of insufficient duration (<6 weeks after date of the first dose without further evaluable tumor assessments).
- PD >12 weeks after date of the first dose (ie, tumor assessment of PD was >12 weeks after date of the first dose and there was no tumor assessment in between).

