### Progression-free Survival (PFS)

- Analysis set: Response Evaluable

Progression-free survival (PFS) is defined as the time from date of the first dose of study treatment to the earliest documented disease progression by Investigator assessment, or death due to any cause, whichever occurs first. If a patient has not had a PFS event at the time of the analysis cutoff or at the start of any new anticancer therapy, PFS is censored at the date of last adequate tumor assessment.

PFS will be calculated as follows:

$$\text{PFS (months)} = (\text{date of event or censoring} - \text{date of first dose} + 1) / 30.4375$$

The censoring and event date options to be considered for PFS analysis are presented in Table 2.

PFS time will be estimated using the Kaplan-Meier method. The PFS rate at 3, 6, 9, 12, 15 and 18 months will be estimated with corresponding 2-sided 95% CIs.

Frequency (number and percentage) of participants with each event type (PD or death) and censoring reasons will be presented along with the overall event and censor rates. Reasons for censoring will be summarized according to the categories in [Table 3](#). In addition, time to progression/censoring, event, and censoring reasons will be listed.

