**Table 2 PFS and DOR Outcome and Event Dates**

Situation	Date of Progression/Censoring	Outcome
No adequate baseline assessment a	Date of first dose a	Censored a
PD or death - after at most one missing or inadequate postbaseline tumor assessment, or - $\leq 8$ weeks ( $\pm 3$ -day window) after date of first dose	Date of PD or death	Event
PD or death - after $\geq 2$ missing or inadequate postbaseline tumor assessment	Date of last adequate tumor assessment b documenting no PD prior to new anticancer therapy, or missed tumor assessments	
No PD		Censored
New anticancer therapy given prior to PD or death		

a This criterion only applies to PFS censoring. If the participant dies  $\leq 6$  weeks after date of first dose and did not initiate new anticancer therapy, the death is an event with date on death date (6 weeks is 2 times the length of the first 2 tumor assessment intervals).

b If there are no adequate post-baseline assessments prior to the PD or death, then the time without adequate assessment should be measured from the date of first dose; if the criteria is met, the censoring will be on the date of first dose.

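### The SAP's Response Evaluable set drops never-scanned participants whom the protocol includes, which can only raise Part 2 ORR and PFS or leave them unchanged; its ORR and DOR text also carries intracranial criteria absent from the protocol

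*SAP*

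**What the plan says.** **Analysis set.** Protocol 9.2 admits a participant to the Response Evaluable Set on one dose plus an adequate baseline disease assessment, and adds: "Participants who discontinued early or died will be included". SAP Table 1 keeps the name but admits only those who "had measurable disease at baseline and at least one post baseline disease assessment". The inclusion sentence is gone.

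The SAP uses this set for ORR, DoR, PFS and TTP in Part 2 (3.2 and 6.2.4; the PFS subsection states "Analysis set: Response Evaluable") and for ORR and PFS in Part 1 (3.3 and 6.3).

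**Rules that presuppose a wider set.** These are all in SAP 6.2.4.
- Among the reasons for a best overall response of NE, one reads "No post-baseline assessments due to early death, i.e., death prior to 6 weeks after" the start date. Others cover no post-baseline scan because of COVID-19 or for other causes.
- PFS Table 2 makes death within about 8 weeks of first dose an event. Its footnote b begins "If there are no adequate post-baseline assessments prior to the PD or death" and measures the unassessed interval from first dose.
- The Non-CR/non-PD category is "applicable only to patients with non-measurable disease at baseline". Protocol 5.1, criterion 4, says that in Part 1 "participants with metastatic HR+ HER2- breast cancer with non-measurable but evaluable disease may be eligible" with the sponsor's approval.

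**Response criteria.** SAP 6.2.4 defines ORR by mRECIST v1.1 (RANO for glioblastoma) for intracranial disease and RECIST v1.1 for extracranial disease. It derives DOR for intracranial/RANO response, extracranial response and ORR. Protocol Sections 3 and 8.1.1 and Appendices 12 and 13 give only RECIST v1.1 and irRECIST. So do SAP 2.2, 3.2 and 5.2.1.

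**The concern.** Two definitions under one name cannot both be programmed, and the choice affects the result. A participant never scanned after baseline cannot be a responder, so removing that participant shrinks the ORR denominator and leaves the numerator alone. If the participant died before any scan, a PFS event disappears as well.

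Part 2 has about 20 participants per cohort and is meant to show early efficacy signals, which feed the recommended Phase 2 dose decision (Protocol 4.3.9). The first scheduled scan is at 8 weeks, so early unscanned loss is plausible. No planned ORR or PFS analysis brings these participants back: the Full Analysis Set serves only OS among the efficacy endpoints, and the mITT population also needs a post-baseline assessment.

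The intracranial text is a separate fault. Treated, stable brain metastases are eligible (Protocol 5.1, criterion 13) and head imaging is required (8.1.1). The SAP does not say how two compartments judged by different criteria combine into one ORR.

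**Working it through.** The documents state no expected ORR, never-scanned rate or power, so there is no figure of theirs to reproduce beyond 3 cohorts × 20 = 60 for Part 2.

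**Who is lost.** Protocol 8.1.1 also requires scans at suspected progression and at withdrawal, unless one was done in the previous 4 weeks. Participants scanned then stay in the SAP set. In Part 2, criterion 4 already requires a measurable lesion, so only those never scanned after baseline are lost. In Part 1, participants with non-measurable disease are lost as well.

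**ORR.** Let r be responders and k the never-scanned among 20. The protocol set gives r/20 and the SAP set r/(20−k), so a non-zero ORR is multiplied by 20/(20−k). With r = 4 assumed and Clopper-Pearson 95% intervals (the method in SAP 5.2.1):

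| k | ORR | 95% CI |
|---|---|---|
| 0 (protocol set) | 4/20 = 20.0% | 5.7–43.7 |
| 1 | 4/19 = 21.1% | 6.1–45.6 |
| 2 | 4/18 = 22.2% | 6.4–47.6 |
| 4 | 4/16 = 25.0% | 7.3–52.4 |
| 5 | 4/15 = 26.7% | 7.8–55.1 |

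With r = 2, 10.0% becomes 2/18 = 11.1% at k = 2 and 2/15 = 13.3% at k = 5.

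**PFS at 3 months (day 91).** Assume k = 4, of whom d die unscanned at day 30 (events under Table 2) and 4−d drop out unscanned (censored at first dose). Of the 16 scanned, 8 progress at day 56 and 8 are followed past day 91.
- SAP set: 8/16 = 50.0%, whatever d is.
- Protocol set: [16/(16+d)] × [8/16], that is, the SAP estimate × (20−k)/(20−k+d).

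| d | Protocol set | SAP set |
|---|---|---|
| 0 | 50.0% | 50.0% |
| 1 | 47.1% | 50.0% |
| 2 | 44.4% | 50.0% |
| 3 | 42.1% | 50.0% |
| 4 | 40.0% | 50.0% |

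Only unscanned deaths move PFS; unscanned drop-outs without an event do not. In a milder case with k = d = 2 and 8 events among the other 18, the protocol set gives 10/20 = 50.0% and the SAP set 10/18 = 55.6%.

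**How likely is k ≥ 1?** If each participant has probability p of never being scanned, the chance that a cohort of 20 loses at least one is 1 − (1−p)^20: 64% at p = 5%, 88% at 10% and 96% at 15%, with expected k of 1, 2 and 3.

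**DoR and TTP.** DoR is unchanged, because a never-scanned participant is not a responder. TTP is nearly unchanged: with no documented progression, such a participant would be censored at or near first dose, so mainly the reported N differs.

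**Measurable disease in Part 1.** This has no fixed direction. Protocol Table 19 lets a participant with non-target disease only reach CR. If one of 2 responders among 6 had non-measurable disease, excluding that participant would lower ORR from 2/6 = 33.3% to 1/5 = 20.0%.

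**The case against.** Protocol Section 9 lets the SAP modify planned analyses and demands an amendment only for major changes to primary endpoints. ORR and PFS are secondary in Part 2 and exploratory in Part 1, and no hypothesis is tested. OS on the Full Analysis Set keeps early deaths, death and progression dates are listed, and summary tables show the number missing. Entry criteria (ECOG 0–1, no short-term life-threatening visceral spread) make 4 unscanned deaths in 20 an extreme case. An empty NE category is not in itself a contradiction, and footnote b still works for participants whose scans were inadequate. The intended response criteria can be recovered from other SAP sections.

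Much of this stands as a limit on size. The narrower set is not barred, the magnitudes are assumed, and the intracranial text has no shown direction of bias. It does not rescue the definition. The SAP presents itself as adding detail to the protocol's analyses and neither flags nor justifies the change. Its NE reasons for absent scans and its early-death rule fit the protocol's set. The direction of the Part 2 bias in ORR and PFS needs no assumption.

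Two further points against the remedy are fair. The protocol set requires an adequate baseline, so the SAP's rules for an inadequate baseline stay unused. And Appendix 13 counts only measurable lesions for irRECIST, so participants with non-measurable disease need their own rule there.

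**Conclusion.** The concern holds. SAP Table 1 and Protocol 9.2 define the same-named set incompatibly, and the SAP version conflicts with its own response and PFS rules. In Part 2 the effect on ORR and PFS is upward or nil: a factor of 20/(20−k) on ORR, and the loss of every unscanned early death from PFS. Under the assumed counts that is about 1 to 7 percentage points of ORR for k = 1 to 5 with 4 responders (21.1 − 20.0 up to 26.7 − 20.0), and up to 10 points of 3-month PFS in the extreme case of 4 unscanned deaths. The values of k and d, the responder counts, the 8 of 16 progressing and the never-scanned rates are all assumptions. DoR and TTP are essentially unaffected. The measurable-disease condition matters only in Part 1, in no fixed direction.

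The intracranial mRECIST/RANO wording is a second, independent error. It leaves ORR and DOR ambiguous and does not touch PFS.

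Both should be corrected before the Part 2 efficacy analysis, although the endpoints are secondary and untested.

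**What to change.** 1. In SAP Table 1, restore the Protocol 9.2 definition: at least one dose and an adequate baseline assessment, with early deaths and discontinuations kept, and no measurable-disease or post-baseline condition.
2. In 6.2.4, state that participants with no post-baseline scan have a best overall response of NE and count as non-responders in the ORR denominator, and that early deaths are PFS events under Table 2.
3. Define ORR as investigator-assessed confirmed CR or PR by RECIST v1.1 and, separately, confirmed irCR or irPR by irRECIST. Delete the mRECIST, RANO, intracranial and extracranial wording from ORR and DOR.
4. Say how Part 1 participants with non-measurable disease are handled under irRECIST, and tidy the rules for an inadequate baseline that the set cannot reach.

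If the sponsor wants the narrower set, it can be a separately named sensitivity analysis with a stated reason. The cost is SAP wording only, with no new data. Reported ORR and PFS may be slightly less favourable.

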## 5.GENERAL METHODOLOGY AND CONVENTIONS

### 5.1 Hypotheses and Decision Rules

There will be no formal hypothesis testing in this study.

### 5.2 General Methods

The data are summarized by dose level cohort, defined by the initial dose of the study intervention administered to participants. DLT rates at the study dose levels will be presented via mean and medians and a Bayesian credible interval based on the posterior density from the full probability model. This information will also be used for the dose escalation decision meetings. Unless otherwise specified, all other summaries will be presented by dose level cohort and overall. Additionally, summary tables will include the total sample size and number missing/not reported. Lastly, missing data may be imputed according to section 0 and unless otherwise specified missing values that are not imputed will be excluded from the analysis.

